**-Standardized ultra-conservative Or Physician-directed ICD programming for SHOCK reduction among patients on continuous flow LVAD support: a randomized controlled trial (STOP SHOCK LVAD study)**

Study Design	Randomized unblinded clinical trial
Planned Number of Patients	280 patients; 140 per treatment arm
Randomization Method	REDCap
Treatment Arms	A) Ultraconservative ICD programming for maximal shock avoidance (see table at end of protocol)  B) Physician Discretion
Primary Endpoints	Any ICD shock Mortality Syncope
Secondary Endpoints	Time to first ICD shock Time to first ICD shock for VT/VF Quality of Life questionnaire Hospitalizations; including HF and ventricular arrhythmia
Inclusion Criteria	
 
- >18 years of age
 
- Pre-existing ICD
 

Exclusion Criteria	
 
- Non-functional ICD system
 
- Uncontrolled ventricular arrhythmias <math>\leq 7</math> days of enrollment (defined as VT/VF >30 seconds and/or causing hemodynamic instability and/or symptoms or pre-syncope or syncope)
 

Follow-up schedule	Routine post-LVAD care; no additional study visits  Remote ICD monitoring encouraged
Study Duration	2 years

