## **INTRODUCTION**

The proposed study will evaluate the utilization of an ultra-conservative programming strategy to reduce shocks for ventricular arrhythmias (VA) in heart failure (HF) patients with an implantable cardioverter-defibrillator (ICD) and a continuous-flow (CF) left ventricular assist device (LVAD). The survival benefit of ICDs with VA detections and therapies enabled has been established in HF patients with reduced ejection fraction (EF) without LVAD, as well as HF patients with older-generation, pulsatile-flow (PF) LVADs. However, newer studies do not demonstrate the same benefit of VA tachy-therapy in patients with current-generation CF LVAD devices, potentially due to better hemodynamic tolerability of VA. In addition, ICD shocks are known to worsen clinical outcomes while causing patients psychosocial harm. Recent studies have applied extended-detection programming to successfully reduce ICD shocks in non-LVAD HF patients. However, shock reduction strategies have not been previously evaluated in LVAD patients in an adequately-powered, randomized clinical trial. This study will prospectively randomize HF patients with pre-existing ICDs to programming at the discretion of their EP provider versus “ultra-conservative” ICD programming, in which a single ventricular fibrillation (VF) zone will be programmed using the maximum rate cutoff allowable across all ICD manufacturers (250 beats per minute [bpm]), as well as the manufacturer-specific maximum detection intervals. In the ultra-conservative arm, a monitor-only zone will be programmed at 150 bpm. The primary endpoint will be the percentage of patients receiving an ICD shock at 2-year follow-up with planned interim analyses at 6 months and 1 year. Secondary endpoints include time to first ICD shock, time to first VT/VF shock, and Quality Life questionnaires. Data collected will include mortality, syncope, LVAD-related hospitalizations (including HF, VA), and the percentage of patients receiving inappropriate ICD shocks at 2-year follow-up. The study hypothesis is that the standardized application of ultra-conservative ICD programming will reduce shocks and improve quality of life without an increase in mortality, syncope, or hospitalizations compared to physician discretion programming in CF LVAD patients.

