## **OBJECTIVES AND ENDPOINTS**

To evaluate the utilization of an “ultra-conservative,” single-zone programming strategy for ICD tachy-therapies in CF LVAD patients as compared to a passive strategy of standard programming (at the discretion of the provider). The study hypothesis is that an ultra-conservative strategy will result in a reduction in shocks and an improvement in quality of life without increasing adverse outcomes including death, hospitalization, and syncope among patients on CF LVAD support.

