### *Sample Size*

The projected sample size is 280 enrolled subjects, 140 randomized to each programming arm. Prior observed ICD shock rates in similar CF LVAD + ICD cohorts were 21% over 11 month follow-up in a study by Richardson et al [27] and 13% over 15 month follow-up in the aforementioned internal study currently under review by Kiehl et al. We thus projected an annual ICD shock incidence of 17% (the mean of the prior 2 studies). Thus, in order to detect a 15% absolute risk reduction in shocks over 2-year follow-up with 80% power and two-tailed  $\alpha=0.05$ , 280 patients are needed.

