### *Statistical Plan*

At the end of study enrollment, baseline characteristics will be compared with potential covariates of interest able to later be balanced either via multi-variable regression or propensity analysis if needed. For continuous outcomes, linear regression will be utilized, for categorical outcomes, logistic regression will be utilized, and for time to event outcomes, Cox regression will be utilized.

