## **Enrollment and Informed Consent**

The multi-disciplinary study investigators include physicians and nurse practitioners in electrophysiology, HF, and cardiothoracic surgery. The LVAD nurse practitioners, HF physicians, and surgical team will identify eligible patients and hold a preliminary discussion with patients about the study. A research coordinator will then verify eligibility, obtain informed consent, complete randomization, direct the device clinic on assigned programming changes (if any), and coordinate research follow-up visits to coincide with clinical LVAD visits for data collection on ICD therapies, symptomatology, HF hospitalizations, and death/transplantation.

All subjects who complete the informed consent process, sign and date the informed consent form are considered enrolled in the Stop Shock LVAD study. Subjects enrolled in this investigation must be followed per protocol.

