## **Randomization**

Randomization to ultra-conservative versus standard programming will occur at the time of study enrollment using REDCap. Randomization will be a 1:1 ratio. Neither the patient nor treatment team are blinded to the randomization or programming assignment. ICD re-programming will occur in the device clinic or patient hospital room as per the current routine care pathway.

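### No model is assigned to hospitalizations, which repeat and are cut short by death and transplant; any/none or raw-count analysis would modestly flatter an arm with more deaths, and first-event Cox loses power

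*Combined protocol and SAP*

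**What the plan says.** The synopsis table lists among the secondary endpoints "Hospitalizations; including HF and ventricular arrhythmia". Objectives and Endpoints makes hospitalization one of three outcomes in the safety half of the hypothesis: fewer shocks and better quality of life "without increasing adverse outcomes including death, hospitalization, and syncope among patients on CF LVAD support". The Introduction leaves hospitalization out of its own list of secondary endpoints and names it as collected data: "Data collected will include mortality, syncope, LVAD-related hospitalizations (including HF, VA". Enrollment and Informed Consent describes "data collection on ICD therapies, symptomatology, HF hospitalizations, and death/transplantation".

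The Statistical Plan section is the whole analysis plan. It matches a model to a type of outcome: linear for continuous, then "for categorical outcomes, logistic regression will be utilized, and for time to event outcomes, Cox regression will be utilized". No section states whether hospitalization is any/none, time to first admission or a number of admissions. None names a count or repeat-event method, a follow-up offset, or a rule for death and transplant in this analysis. The Sample Size section concerns shocks only; no margin or power is given for hospitalization.

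**The concern.** A patient on LVAD support can be admitted several times in 2 years, and death or transplant ends the time in which that can happen. The three listed models, in their ordinary form, handle this differently:

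- Logistic regression on any admission ignores both repeat admissions and time at risk. A patient who dies early without an admission counts as a good result.
- Linear regression on the count keeps repeat admissions but ignores time at risk.
- Cox regression on the first admission respects time at risk but drops every later admission.

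At stake is a claim of no increase. If the ultra-conservative arm had more deaths, the first two analyses would shift toward that claim simply because there was less time to be admitted. Under the third, a non-significant result could be read as reassurance when the analysis had limited power. Because the form is open and the trial is unblinded, it could also be chosen after results by arm are known.

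**Working it through.** **The plan's own figure.** The only sample-size figure is for shocks: "The projected sample size is 280 enrolled subjects, 140 randomized to each programming arm", based on "We thus projected an annual ICD shock incidence of 17% (the mean of the prior 2 studies". Doubling gives 2 × 17% = 34% at 2 years, and 34% − 15% = 19% in the ultra-conservative arm. Power with 140 per arm is 81.5%, and 80% power needs 270 in total, so the stated design reproduces. It says nothing about hospitalization.

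**Inputs.** From the documents: 140 per arm, 1:1 allocation, 2 years. The documents give no admission, death or transplant rates, so these are assumptions. Base case: 1 admission per patient-year in control, gamma between-patient variance k = 0.7, and 2-year mortality of 30% (ultra-conservative) versus 20% (control).

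**Step 1: bias with equal true admission rates.** With exponential death, the hazard is h = −ln(1 − p)/2 and mean follow-up over 2 years is p/h.

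- Ultra-conservative: h = 0.178, mean follow-up 0.30/0.178 = 1.68 years.
- Control: h = 0.112, mean follow-up 0.20/0.112 = 1.79 years.
- At 1 admission per patient-year, the ratio of mean counts is 1.68/1.79 = 0.94, or 6% fewer admissions from lost time alone.
- A patient observed for t years at rate r has no admission with probability (1 + k·r·t)^(−1/k). Averaging over follow-up gives 63.7% versus 66.4% admitted, a difference of 2.7 points.
- The standard error of that difference is √(0.637 × 0.363/140 + 0.664 × 0.336/140) = 5.7 points, so the shift is about half a standard error.

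**Step 2: which models carry the bias.** Large-sample estimates, no true difference, 2-year deaths 40% versus 20%, transplant 30% in both arms, 1 admission per patient-year, variance 1:

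| Summary (ultra-conservative vs control) | Death unrelated to admission risk | Death and admission share one frailty |
|---|---|---|
| Any/none odds ratio | 0.85 | 0.85 |
| Ratio of mean counts | 0.88 | 0.82 |
| First-event Cox hazard ratio | 1.00 | 0.97 |
| Ratio of rates per patient-year | 1.00 | 0.91 |

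The any/none and raw-count summaries flatter the arm with more deaths. Cox censored at death is nearly unaffected. The rate ratio is unbiased only if death is unrelated to admission risk.

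**Step 3: power to see a real rise.** Simulated trials with a true rate 40% higher in the ultra-conservative arm, mortality 30% versus 20%, rejecting in the harmful direction at two-sided 0.05. A two-proportion test stands in for logistic and a log-rank test for Cox; the rate model is robust Poisson with a log-time offset.

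| Scenario | Any/none | First-event Cox | Linear on counts | Rate model |
|---|---|---|---|---|
| Base case | 14% | 38% | 46% | 70% |
| Adding 30% transplant and shared frailty | 16% | 34% | 37% | 58% |
| 0.2 admissions per patient-year | 17% | 27% | 24% | 35% |
| 0.1 admissions per patient-year | 13% | 19% | 16% | 22% |

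Repeat runs of the base case stayed within 14–15%, 38–41%, 46–53% and 70–74%. Across 0.5 to 1.5 admissions per patient-year and variance 0.3 to 1.0, the ranges were 10–22%, 31–56%, 34–75% and 50–94%.

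**The case against.** The strongest reply is that the plan has not committed to a wrong method. It maps models to outcome types and never assigns one to hospitalization, and Cox regression can be extended to repeat events. That stands: the defect is an open choice, and two of the natural choices are poor.

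Three stronger readings are tempting, and the documents do not support them.

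- A reader might infer that the arm with more deaths looks safer under every listed model. Step 2 shows otherwise for Cox. For the other two, the shift is small and needs a mortality gap that the documents neither give nor predict. Mortality is also listed under the primary endpoints, so a gap would be seen.
- A reader might infer that the model choice alone will cause a real rise to be missed. That depends on the admission rate, which the documents do not give. At 0.1 to 0.2 per patient-year even the rate model has only 22–35% power, and there the limit is mainly sample size. First-event Cox also keeps more than half of the rate model's power in the base case (38/70 = 54%).
- A reader might infer that a rate model cures the problem. With shared frailty and 40% versus 20% deaths it gives 0.91 when the truth is 1.

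It is also fair to say that all-cause admissions are not clearly collected: the text names LVAD-related, HF and VA admissions. This point does not depend on them.

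**Conclusion.** The concern holds as a gap in specification with a better and inexpensive method available. The trial rests part of its no-harm claim on hospitalization, but the plan fixes neither the form of that endpoint nor the handling of death and transplant. The directional bias is modest, confined to any/none and raw-count analyses, and conditional on the assumed 10-point mortality excess. The power loss from first-event Cox is larger, 38% against 70% in the base case, but it too rests on assumed rates and narrows as admissions become rarer. The rate model had the most power in each scenario of Step 3, including with transplant and shared frailty, so the recommendation is firmer than any single percentage. This should be settled before hospitalization data are examined by arm; it does not affect the shock endpoint.

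**What to change.** Add to the Statistical Plan:

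- Hospitalizations of the kinds already named for collection (LVAD-related, including HF and VA) are analysed as admissions per patient-year alive on LVAD support, with a negative binomial or robust Poisson model and log follow-up time as offset.
- The rate ratio and 95% CI are reported beside the numbers of deaths and transplants in each arm.
- A sensitivity analysis treats death as a terminal event: mean cumulative admissions to 24 months, a joint model of admissions and death, or admissions plus death.

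The cost is a few sentences, a little more analysis, and a summary measure less familiar than a percentage. Design, sample size and care do not change. Hospitalization, death and transplant data are already named for collection; the sponsor need only confirm that the number of admissions, and the dates of death and transplant, are captured for each patient.

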### *Study Population*

Patients will be eligible for study enrollment and randomization if adult (>18 years old) with a pre-existing, active ICD prior to CF LVAD implantation. Possible study enrollment will be discussed with eligible patients by their treating medical teams and the dedicated study research coordinator during

their index LVAD hospitalization. Consent and randomization will occur either at the time of index hospitalization discharge or during the first post-discharge LVAD/ICD clinic visit, whichever comes first.

*Inclusion:*

- >18 years of age
- Pre-existing ICD

*Exclusion:*

- Non-functional ICD system
- Uncontrolled ventricular arrhythmias  $\leq 7$  days of enrollment (defined as VT/VF  $>30$  seconds and/or causing hemodynamic instability and/or symptoms or pre-syncope or syncope)

Of note, the need for anti-arrhythmic (AAT) drug therapy and/or catheter ablation is not an exclusion criteria, with treatment of VA per treatment team discretion and non-protocol driven. Ventricular ectopy and/or palpitations associated with non-sustained VT also do not serve as an exclusion criteria.

## **Enrollment and Informed Consent**

The multi-disciplinary study investigators include physicians and nurse practitioners in electrophysiology, HF, and cardiothoracic surgery. The LVAD nurse practitioners, HF physicians, and surgical team will identify eligible patients and hold a preliminary discussion with patients about the study. A research coordinator will then verify eligibility, obtain informed consent, complete randomization, direct the device clinic on assigned programming changes (if any), and coordinate research follow-up visits to coincide with clinical LVAD visits for data collection on ICD therapies, symptomatology, HF hospitalizations, and death/transplantation.

All subjects who complete the informed consent process, sign and date the informed consent form are considered enrolled in the Stop Shock LVAD study. Subjects enrolled in this investigation must be followed per protocol.

## **Randomization**

Randomization to ultra-conservative versus standard programming will occur at the time of study enrollment using REDCap. Randomization will be a 1:1 ratio. Neither the patient nor treatment team are blinded to the randomization or programming assignment. ICD re-programming will occur in the device clinic or patient hospital room as per the current routine care pathway.

## **ICD Programming**

There will be no study-related diagnostic tests, treatments, or follow-up visits beyond routine post LVAD care. The ICD re-programming will be performed during the routine pre-discharge ICD check during the LVAD implant hospitalization or at routine LVAD clinic follow-up  $\leq 30$  days. For patients experiencing sustained VA below the VT zone in the ultra-conservative pathway, a symptom-driven care pathway will be implemented involving same-day cardioversion with the associated routine care. In the physician-discretion arm, ICD shocks delivered for VA routinely result in emergency department visits and hospitalizations, which fall under usual care covered by private and public payers.

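### Nothing ties ICD re-programming to randomisation, so an unknown share of arm A may spend up to about 30 days on previous settings, modestly diluting the shock comparison

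*Combined protocol and SAP*

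**What the plan says.** Four sections of the combined protocol and SAP bear on timing.

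- **Study Population:** "Consent and randomization will occur either at the time of index hospitalization discharge or during the first post-discharge LVAD/ICD clinic visit, whichever comes first". Taken literally, discharge always precedes the first visit after it, but the clinic visit is clearly meant as a second route.
- **Randomization:** "Randomization to ultra-conservative versus standard programming will occur at the time of study enrollment using REDCap". It also says "ICD re-programming will occur in the device clinic or patient hospital room as per the current routine care pathway".
- **Enrollment and Informed Consent:** a patient who has signed consent counts as enrolled. The coordinator obtains consent, then randomises, then instructs the device clinic. The order is fixed; no interval is given.
- **ICD Programming:** "The ICD re-programming will be performed during the routine pre-discharge ICD check during the LVAD implant hospitalization or at routine LVAD clinic follow-up", with a limit of 30 days on the clinic option. What the 30 days run from is not stated.

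On the outcome, the Introduction says "The primary endpoint will be the percentage of patients receiving an ICD shock at 2-year follow-up". The Statistical Plan says "for categorical outcomes, logistic regression will be utilized, and for time to event outcomes, Cox regression will be utilized". Neither defines day 0, the analysis set, or how a shock between randomisation and re-programming is counted. The Follow Up table puts randomisation in the enrolment column and, as it reads in the available text, first marks device interrogation at 1 month.

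**The concern.** A patient can be randomised to arm A at discharge, after the routine pre-discharge device check is over, and go home with unchanged settings until a clinic visit. The protocol permits this and has no rule for it.

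During the gap such a patient has roughly the control arm's risk of shock. If the 2-year clock starts at randomisation and patients are analysed as randomised, shocks in the gap are charged to a strategy not yet applied. The 2-year difference shrinks, and for time to first shock the two arms have similar hazards at the start. The study also hopes to show no increase in mortality, syncope or hospitalisation, and time without the assigned settings would mute a difference there too. Finally, with no counting rule in an unblinded trial, the handling of these shocks could be settled after the data are seen.

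**Working it through.** **Inputs from the Sample Size section.** Annual shock incidence 17%; absolute reduction 15 points at 2 years; 80% power; two-sided alpha 0.05; 140 per arm. The section does not say how 17% per year becomes a 2-year risk, so both readings are carried:

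- doubled: 2 × 17% = 34%, against 19%
- compounded: 1 − 0.83² = 31.1%, against 16.1%

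**The plan's own figure.** The pooled-variance formula for two proportions gives these totals:

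| 2-year risks | No continuity correction | With correction |
|---|---|---|
| 34% v 19% | 270 | 296 |
| 31.1% v 16.1% | 250 | 276 |

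The stated 280 is reproduced to within 3% by 276. Power at 140 per arm, without correction, is Φ[(d − 1.96·SE₀)/SE₁], where SE₀ is pooled and SE₁ unpooled:

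- 34% v 19%: (0.150 − 1.96 × 0.05275)/0.05198 = 0.897, power 81.5%
- 31.1% v 16.1%: (0.150 − 1.96 × 0.05076)/0.04996 = 1.011, power 84.4%

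**Delay model (assumptions).** Constant shock hazards; previous settings carry the control hazard; every arm A patient waits one month of 24; no death, transplant or dropout, since the plan states no allowance.

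For 34% v 19%:
- control hazard = −ln(0.66)/24 = 0.0173 per month
- arm A hazard = −ln(0.81)/24 = 0.00878 per month
- arm A 2-year risk with delay = 1 − exp[−(0.0173 + 23 × 0.00878)] = 19.7%
- difference = 34.0 − 19.7 = 14.3 points
- extra arm A patients with a shock = 140 × (0.1969 − 0.1900) ≈ 1
- power = Φ[(0.1431 − 1.96 × 0.05297)/0.05227] = Φ(0.752) = 77.4% (77.5% if the gap is counted as 30 of 730 days)

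For 31.1% v 16.1%:
- hazards = −ln(0.6889)/24 = 0.0155 and −ln(0.8389)/24 = 0.00732 per month
- arm A 2-year risk with delay = 1 − exp[−(0.0155 + 23 × 0.00732)] = 16.8%
- difference = 31.1 − 16.8 = 14.3 points, again about one extra patient
- power = 80.5%

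**Half of arm A delayed.** Arm A risk is the average of the delayed and undelayed risks, the difference is 14.7 points, and power is 79.5% (34% base) or 82.5% (31.1% base).

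**The case against.** The strongest reply is that the sections can be read as paired routes: discharge goes with the pre-discharge check, and the first clinic visit goes with clinic re-programming. Re-programming in the hospital room is expressly allowed. On that reading there is little or no gap. The trial also adds no visits to routine care, so some delay in delivering a strategy is a defensible pragmatic choice, and for shock reduction the resulting bias is conservative. All of this stands as a limit on size. It does not close the gap, because no section requires the pairing.

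Some stronger readings are tempting but unsupported:

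- **That arm A as a whole starts on old settings.** The gap is permitted, not general, and the documents do not give the share delayed.
- **That gap shocks certainly count against arm A.** The Follow Up table suggests a clock starting at enrolment, but neither day 0 nor the analysis set is defined in words.
- **That settings could be changed before consent.** Enrollment and Informed Consent fixes the order as consent, randomisation, then programming.
- **That the unblinded team would withhold the assignment after an early shock.** The documents give no evidence of this.
- **That the loss is 2 to 3 points or more.** This needs a first-month hazard of 3 to 5 times the later one, for which the documents offer no source. Adding it also lifts the control risk to 36.2% or 38.4% and the undelayed difference to 15.8 or 16.6 points, so such losses cannot be subtracted from 15.0.

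**Conclusion.** The concern holds in limited form. Randomisation and re-programming run on separate clocks, the 30-day limit has no stated origin, and shocks in between have no counting rule.

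The direction is toward no difference, for benefit and possibly for harm. Even if all of arm A were delayed, the cost under constant hazards is 0.7 points of effect and about 4 points of power. That takes power below the planned 80% on the 34% base and leaves it just above on the 31.1% base. With half delayed, the cost is about 2 points of power. These figures assume control-like risk on previous settings and analysis as randomised from randomisation. A larger loss would require shocks concentrated in the first month.

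The change is worth making because it is cheap and removes the dilution at source.

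**What to change.** Reconcile Study Population, Enrollment and Informed Consent, Randomization, and ICD Programming as follows:

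1. Allow consent earlier, but perform the REDCap randomisation at the existing routine device check, pre-discharge or first clinic, at which the assigned settings can be applied. Confirm eligibility that day.
2. Amend Enrollment and Informed Consent, and the matching sentence in Randomization, so that consent alone is not the point of randomisation. At present consent means enrolment and enrolment means randomisation, so changing only one section would create a new contradiction.
3. Keep the existing 30-day outer limit and state what it runs from.
4. In the Statistical Plan, define day 0 as randomisation in both arms, analyse as randomised, and record the date of re-programming.
5. Do not drop pre-programming shocks from arm A alone. That would give one arm an artificially shock-free period.
6. If any gap remains, pre-specify a sensitivity analysis from a common day-30 landmark in both arms.

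The cost is protocol wording and coordinator timing; no device check is added. Some patients would be randomised at the first clinic visit instead of at discharge, and a few who have consented may become ineligible before randomisation.

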## **Study Rationale**

The current International Society for Heart and Lung Transplantation (ISHLT) guidelines provide a class I recommendation for tachy-therapy re-activation in patients with ICDs undergoing LVAD implantation [1]. However, these guidelines reflect a survival benefit observed in cohorts comprised primarily of older-generation PF LVADs [2, 3]. While the overall VA prevalence in the LVAD population exceeds 50% [4-6] with VA usually occurring >200 beats per minute [7], VA are generally well-tolerated both hemodynamically and symptomatically. Observed LVAD flows do decrease during sustained VA [8, 9], but there are multiple case reports of LVAD patients remaining awake and asymptomatic despite hours of ventricular fibrillation [10-12] and a large case series reported no deaths and rare syncope due to VA in CF LVAD patients [7]. Contrary to guidelines, contemporary evaluations restricted to CF LVADs show no clear ICD survival benefit in single center studies [7, 13] nor a large, pooled meta-analysis [14]. In fact, propensity-matched analyses of CF LVAD patients in the INTERMACS [15] and UNOS [16] registries have demonstrated increased mortality and more hospitalizations among patients with an active ICD and treated VA.

It is unclear in the CF LVAD population whether ICD shocks themselves are harmful or rather identify a higher-acuity patient subgroup. In the general HF population, however, shocks have consistently been associated with worse outcomes [17-21]. Shock reduction programming resulted in reduced mortality in the MADIT-RIT trial [22], suggesting shocks may be directly harmful and not only a marker of substrate

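### External cardioversion is a named care route in the ultra-conservative arm, but no endpoint, listed data item, scheduled assessment or planned analysis counts it by arm

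*Combined protocol and SAP*

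**What the plan says.** **Intervention.** The Introduction says that in the ultra-conservative arm "a single ventricular fibrillation (VF) zone will be programmed using the maximum rate cutoff allowable across all ICD manufacturers", given as 250 bpm, with a monitor-only zone at 150 bpm. In the supplemental table of initial programming, VT detection and therapy are off for every vendor. The VF zone still delivers antitachycardia pacing and shocks.

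**Route for untreated VA.** For sustained VA below the treated range in this arm, the ICD Programming section states that "a symptom-driven care pathway will be implemented involving same-day cardioversion with the associated routine care". The next sentence says that shocks for VA in the physician-discretion arm usually lead to emergency department visits and admissions. The second supplemental table gives one re-programming trigger per arm: a shock without symptoms in the standard arm, and symptoms leading to external cardioversion in the ultra-conservative arm.

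**What is measured.** The Introduction states: "The primary endpoint will be the percentage of patients receiving an ICD shock at 2-year follow-up". The synopsis lists any ICD shock, mortality and syncope as primary. Its secondary list has time to first ICD shock, time to first ICD shock for VT/VF, quality of life and "Hospitalizations; including HF and ventricular arrhythmia". The Introduction adds: "Data collected will include mortality, syncope, LVAD-related hospitalizations (including HF, VA), and the percentage of patients receiving inappropriate ICD shocks". Enrollment and Informed Consent lists ICD therapies, symptomatology, HF hospitalizations and death or transplantation. The Follow Up schedule has AE/SAE/QOL assessment and device data. The Statistical Plan assigns linear, logistic or Cox regression by type of outcome.

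**The concern.** The intervention withholds device therapy for arrhythmias that the control arm may treat, and the protocol names an external procedure as part of the response when they cause symptoms. That procedure is the nearest substitute for the event that the primary endpoint counts, and it is counted nowhere. The trial could report fewer ICD shocks without showing how many of the patients concerned were shocked externally instead.

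The hospitalization endpoint does not reliably close the gap. By the protocol's own account, a control-arm shock tends to produce an emergency visit and an admission, whereas the corresponding event in the other arm is a same-day procedure, which need not be an admission. The endpoint could record the consequence in one arm and miss it in the other.

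The paired re-programming triggers show the same imbalance. The standard-arm trigger is itself a primary-endpoint event. The ultra-conservative trigger is not an endpoint event of any kind.

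**Working it through.** **1. Where cardioversion appears.** It is mentioned in two places only: the ICD Programming section and the trigger line of the second supplemental table. Against these:

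| Place | What is named | External cardioversion? |
|---|---|---|
| Synopsis and Introduction, endpoints | ICD shock, mortality, syncope, times to ICD shock, quality of life, hospitalizations | No |
| Introduction and Enrollment, data lists | Mortality, syncope, hospitalizations, inappropriate ICD shocks, ICD therapies, symptomatology, transplantation | No |
| Follow Up schedule | AE/SAE/QOL, device interrogation | No |
| Statistical Plan | Regression by outcome type | No |

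The monitor zone and interrogation bear on the untreated arrhythmia and on device therapy. Nothing says that they record an external shock.

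**2. The plan's own figure.** Inputs from Sample Size: 17% ICD shock incidence per year, a 15-point absolute reduction over 2 years, 80% power, two-tailed alpha 0.05, 140 per arm. The 2-year control risk is not stated. It is 1 − 0.83² = 31.1% if compounded, or 2 × 17% = 34% if doubled. For two proportions, n per arm = [1.96√(2p̄(1−p̄)) + 0.842√(p₁(1−p₁)+p₂(1−p₂))]² / 0.15².

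- 31.1% vs 16.1%: 125 per arm, or 138 with continuity correction (276 in total, close to 280). Power at 140 per arm is 84.4% without the correction.
- 34% vs 19%: 135 per arm (270), or 148 with continuity correction (296). Power at 140 per arm is 81.5% without the correction.

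The sample size is therefore consistent with its inputs, and this point does not depend on it.

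**3. What the any-route difference depends on.** In each arm, the proportion with any shock = the proportion with an ICD shock + the proportion with an external shock only. Hence

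any-route difference = ICD-shock difference − (external-only in the ultra-conservative arm − external-only in the control arm).

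The plan addresses the first term and gives no means of estimating the second.

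**4. Illustration on assumed values.** The documents supply neither external-only proportion.

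*(a) Net excess as a share of the whole arm.* At 2%, 5% or 10% (2.8, 7 or 14 of 140 patients), 15 points becomes 13, 10 or 5. At 15% (21 patients) it is zero. At 5%, the power of an any-route test with 140 per arm would be 45.3% (34% control risk) or 47.8% (31.1%).

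*(b) Share f of averted-shock patients who are cardioverted externally, with no extra external-only patients in the control arm.* The planned reduction is 0.15 × 140 = 21 patients, and the any-route difference is 15 × (1 − f). The 95% interval is the difference ± 1.96√[(p₁(1−p₁)+p₂(1−p₂))/140].

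| f (assumed) | Patients, 21f | Difference, points | 95% CI, control 34% | 95% CI, control 31.1% |
|---|---|---|---|---|
| 0% | 0 | 15 | 4.8 to 25.2 | 5.2 to 24.8 |
| 10% | 2.1 | 13.5 | 3.2 to 23.8 | 3.6 to 23.4 |
| 25% | 5.25 | 11.25 | 0.8 to 21.7 | 1.1 to 21.4 |
| 50% | 10.5 | 7.5 | −3.2 to 18.2 | −2.9 to 17.9 |

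The half-widths run from 9.8 to 10.7 points. If a quarter of averted shocks were inappropriate (also assumed), and so could not lead to cardioversion for VA, the differences are 15 × (1 − 0.75f) = 15, 13.9, 12.2 and 9.4 points.

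Neither scenario bounds the effect. Both set control-arm external-only events at zero. Scenario (b) also leaves out patients whose VA would otherwise have been ended by device pacing without a shock.

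**The case against.** The strongest reply is that the trial concerns ICD shocks and says so. The hypothesis that "an ultra-conservative strategy will result in a reduction in shocks and an improvement in quality of life" follows directly on an objective about ICD tachy-therapies. The title refers to ICD programming, the sample size to ICD shock incidence, and the cited evidence of harm to ICD shocks. This stands. A reader might infer that the hypothesis promises fewer shocks by any route, but in context the word means ICD shocks. The any-route comparison complements the primary question and is not one that the protocol has failed to answer.

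Second, part of the burden is already covered. Syncope, VA hospitalization and quality of life are endpoints, symptomatology is collected, and AE/SAE assessment may draw on medical records and the registry. Some cardioversions will surface there. What remains is mainly the same-day procedure that is neither admitted nor reported as an adverse event. None of these routes is set up to count cardioversions by arm, so the gap narrows but stays.

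Third, the effect may be small. The Study Rationale says "VA are generally well-tolerated both hemodynamically and symptomatically", treatment of VA is otherwise left to the clinical team, and avoided inappropriate shocks would not lead to cardioversion for VA. This also stands, and it is why no size is claimed.

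Two further inferences should be resisted. The re-programming pathway is not triggered in one arm only, since each arm has a trigger; the difference is that only one of the two triggers is an endpoint event. And the absence of a listed item does not show that the data will go uncollected: the case-report form is not among the documents, so the point is limited to what is pre-specified.

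**Conclusion.** The point holds as a gap in pre-specification. A named substitute for the primary-endpoint event, written into the care pathway of one arm, is not counted by arm anywhere in the plan, and the hospitalization endpoint may miss it unevenly. The primary endpoint remains valid for what it measures.

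The size is unknown. The percentages above are illustrations on assumed rates, and a reader should not infer from them that the planned benefit would shrink by any particular amount, or that it would shrink at all.

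The change should be made, because it is cheap and events left unrecorded may be hard to recover fully later, but the trial does not stand or fall by it. Confidence is medium, since the case-report form is unseen and the cardioversion rate is not given.

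**What to change.** - Keep ICD shock as the primary endpoint and leave the sample size unchanged.
- Record every external cardioversion or defibrillation in both arms: date, rhythm, setting, and whether the patient was admitted.
- Tabulate by arm the patients with ICD shock only, external shock only, both and neither.
- Add first shock by any route (ICD or external) as a secondary estimate with its 95% confidence interval, stated not to be a powered test.
- Word the conclusion as a reduction in ICD shocks, read alongside the any-route result.

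**Cost.** A short repeatable event form in both arms, one table and one extra analysis. The any-route reduction may look smaller than the ICD-only one. The decision to cardiovert is made by a team that knows the assignment (Study Population and Randomization sections), so the any-route result is open to bias from that knowledge, and the report should say so.

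**Separate minor point.** The ICD Programming section defines entry to the pathway by reference to a VT zone, whereas the initial ultra-conservative programming has that zone off; one appears only in the re-programming table. The passages must be reconciled, because the wording decides which events enter the pathway. The main point does not depend on it.
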